- Not castrated if the testosterone level is superior or equal to 50 ng/dL for the test and confirmation test.

HRQoL

- FACT-P

The FACT-P score is composed of 27 general questions about physical, social, emotional, and functional well-being as well as a 12-item questionnaire about prostate-specific concerns. A maximum score of 156 points indicates the highest level of QoL. The total FACT-P score will be calculated as the sum of 39 item scores.

Dimensions	Subscales	Number of items	N° item
General well-being	Physical well-being	7	GP1 to GP7
	Social well-being	7	GS1 to GS7
	Emotional well-being	6	GE1 to GE6
	Functional well-being	7	GF1 to GF7
Prostate-specific concerns	--	12	C2, C6 P1 to P8 BL2 to BL5

For missing data, if less than 50 % of the items are missing, subscale scores will be prorated. This will be done by using the formula below:

Prorated subscale score = (Sum of item scores)*(Number of items in the subscale)/
(Number of items answered).

If more than 50 % of the items are missing from any subscale, the subscale will not be imputed.

For any given scale, if the missing values represent more than 10 % of the population; two analyses will be performed. One analysis using the available values and a second analysis imputing the missing values by the mean value of the available data at the concerned timepoint will be performed.

- SF-36v2

The SF-36 health survey version 2 [1] is composed of 36 items about 8 Health Domain Scales: Physical Functioning (PF), Role-Physical (RP), Bodily Pain (BP), Social Functioning (SF), Mental Health (MH), Role-Emotional (RE), Vitality (VT) and General Health (GH).

All but one of the 36 items (item n°2: self-reported health transition) are used to score the eight raw Health Domain Scales. Each item is used in scoring only one scale. The response for each item is recoded according to the table below.

Then, the eight Health Domain Scales Total Raw Scores are calculated, according to the table on the following page. Each score will range from 0 to 100, where 0 represent the lowest possible score (worst health state) and 100 represent the highest possible score (best health state).

Finally, the eight health domain scales scores are normed to the 2009 U.S. general population to have a mean of 50 and a standard deviation of 10. These are health domain scales norm-based scores.

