Two summary measures are calculated, using the eight health domain scales norm-based scores and an algorithm: an overall score of physical health (Physical Component Summary or PCS) and overall score of mental health (Mental Component Summary or MCS)

Item numbers	Precoded response value	Final response value
3a to 3j	1 2 3	3 2 1
2 4a to 4d 5a, 5b, 5c 9b, 9c, 9f, 9g, 9i 10, 11a, 11c	1 2 3 4 5	5 4 3 2 1
7	1 2 3 4 5 6	6 5 4 3 2 1
1 6 8 9a, ,9d, 9e, 9h 11b, 11d	1 2 3 4 5	5 4 3 2 1

Component Summary measures (calculated from a combination of norm-based scales scores)	Health Domain Scales (raw and norm-based)	Number of items	Items
Physical Health (PCS)	Physical functioning (PF)	10	3a to 3j
	Role-Physical (RP)	4	4a to 4d
	Bodily Pain (BP)	2	7, 8
	General Health (GH)	5	1, 11a to 11d
Mental Health (MCS)	Social Functioning (SF)	2	6, 10
	Mental Health (MH)	5	9b, 9c, 9d, 9f, 9h
	Role-Emotional (RE)	3	5a, 5b, 5c
	Vitality (VT)	4	9a, 9e, 9g, 9i

The derivations of the eight Health Domain Scales Total Scores (Raw and norm-based) and the two component summary measures (calculated from a combination of norm-based scales scores) will be performed using software application delivered by QualityMetric.

Missing data are ignored and the scale is calculated without the missing item. If more than 50 % of the items are missing from any scale, the scale score will not be calculated.

For any given value, if the missing values represent more than 10 % of the population; two analyses will be performed. One analysis using the available values and a second analysis imputing the missing values by the mean value of the available data at the concerned timepoint will be performed.

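### The SF-36v2 recoding table reverses every item, with one mapping for two separately listed five-level groups, and the SAP does not say whether the scoring software receives precoded or recoded answers

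*SAP*

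**What the plan says.** SAP Section 3.2.10 (Derived data, HRQoL, SF-36v2) gives a sequence: recode, then compute eight raw scales, then norm them, then form the two component summaries. The first step reads "The response for each item is recoded according to the table below". The raw scales are to run from 0 to 100, "where 0 represent the lowest possible score (worst health state) and 100 represent the highest possible score (best health state".

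The recoding table has four rows:

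- Items 3a–3j: 1 2 3 becomes 3 2 1.
- Items "2 4a to 4d 5a, 5b, 5c 9b, 9c, 9f, 9g, 9i 10, 11a, 11c": 1 2 3 4 5 becomes 5 4 3 2 1.
- Item 7: 1 to 6 becomes 6 to 1.
- Items "1 6 8 9a, ,9d, 9e, 9h 11b, 11d": 1 2 3 4 5 becomes 5 4 3 2 1.

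A second table assigns items to scales. After it, the SAP says that derivation of the raw and norm-based scales and of the two summaries "will be performed using software application delivered by QualityMetric". It does not say whether that application is given precoded or table-recoded answers.

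**The concern.** The second and fourth rows carry the same mapping. Grouping by number of response levels cannot explain two rows, because items of one question are divided between them: 9b, 9c, 9f, 9g, 9i against 9a, 9d, 9e, 9h, and 11a, 11c against 11b, 11d. The natural reading is that one group should be reversed and the other kept, and that the final values of one row are wrong.

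Four scales (General Health, Social Functioning, Mental Health, Vitality) draw on both rows, so a wrong row would set items within a scale against each other. Separately, a recoding step placed ahead of software that may do its own recoding invites a double reversal.

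HRQoL is a secondary objective (Section 1.1.2). The plan models change on every SF-36v2 measure: 8 raw scales + 8 norm-based scales + 2 summaries = 18. A wrong direction would hide or invert a difference between triptorelin and active surveillance on these measures.

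**Working it through.** **Inputs.** The recoding table, the item-to-scale table and the required direction all come from Section 3.2.10. Item wording is not printed, so each plausible direction of the groups is tried.

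**Item count.** Recoding table: 10 + 16 + 1 + 9 = 36. Scale table: 10 + 4 + 2 + 5 + 2 + 5 + 3 + 4 = 35. The one item left over is item 2, which the SAP says is not scored.

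**Formula (assumed, since the SAP prints none).** With n items, K levels per item and final values f from 1 to K in equal steps, score = 100 × (sum of f − n) / sum of (K − 1).

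**The plan's own figure.** If each item is recoded in its true direction, best health has f = K throughout and scores 100; worst health has f = 1 throughout and scores 0. This is what the SAP requires.

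**Route 1: precoded answers go into the software.** The table is never applied. All scales run 0 to 100 as stated.

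**Route 2: recoded answers go into software that recodes again.** The table replaces each answer x by K + 1 − x. The software's correct recoding either keeps or reverses the item. In both cases the final value is K + 1 minus the correct one, so each score becomes 100 minus the correct score. All eight scales run backwards, with no cancellation. This needs no assumption about item wording.

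**Route 3: the table is the only recoding.** Assume the two five-level rows face opposite ways and item 7 is correctly reversed. Three branches:

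- A: the second row and 3a–3j should not be reversed.
- A2: only the second row should not be reversed.
- B: only the fourth row should not be reversed.

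Arithmetic for best health:

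- Social Functioning, one item from each row: sum 1 + 5 = 6; 100 × (6 − 2)/8 = 50.
- Vitality, two from each: sum 2 + 10 = 12; 100 × (12 − 4)/16 = 50.
- Mental Health, three from the second row and two from the fourth. A: 3 + 10 = 13; 100 × (13 − 5)/20 = 40. B: 15 + 2 = 17; 100 × (17 − 5)/20 = 60.
- General Health, two from the second row and three from the fourth. A: 2 + 15 = 17, giving 60. B: 10 + 3 = 13, giving 40.
- Bodily Pain in B, item 7 at 6 and item 8 at 1: 100 × (7 − 2)/9 = 55.6.

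| Scale | A best/worst | A2 best/worst | B best/worst |
|---|---|---|---|
| Physical Functioning | 0/100 | 100/0 | 100/0 |
| Role-Physical | 0/100 | 0/100 | 100/0 |
| Role-Emotional | 0/100 | 0/100 | 100/0 |
| Social Functioning | 50/50 | 50/50 | 50/50 |
| Vitality | 50/50 | 50/50 | 50/50 |
| Mental Health | 40/60 | 40/60 | 60/40 |
| General Health | 60/40 | 60/40 | 40/60 |
| Bodily Pain | 100/0 | 100/0 | 55.6/44.4 |
| Scales wrong | 7 | 6 | 5 |

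If instead every item truly needs reversal, the table gives 100/0 throughout and the split row is merely redundant.

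**Effect on a treatment difference D in route 3, if all items of a scale shift equally.** A fully reversed scale shows −D. Social Functioning and Vitality show 0. Mental Health and General Health show one fifth of D, with opposite signs.

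**The case against.** The strongest reply is that the SAP gives scoring, including the raw scales, to the vendor's application. The recode–score–norm sequence can then be read as a description of how the instrument works, not as a pre-processing order. On that reading precoded answers go in and nothing is wrong. This stands as one possible route and is why a scoring error is not established. It does not remove the problem: the text says each response is recoded and then scored, and names no input for the software. A programmer who follows the sequence literally ends in route 2 or 3.

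A second reply is that the misdirected row cannot be identified without the item wording. That is correct. A reader might infer that seven of eight scales are wrong and only Bodily Pain escapes, or that a quality-of-life loss will be reported as a gain. The first holds only in branch A of route 3; in branch B Bodily Pain is damaged and Physical Functioning, Role-Physical and Role-Emotional are right. The second holds only for scales that end up reversed.

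Third, a multi-line table can lose or misplace a cell when converted to text, so the final values should be compared with the typeset SAP. This caveat stands.

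Fourth, Section 4.3 requires review of outputs for nonsensical results. That might catch a fully reversed scale, but values clustered around 50 would not look odd. Listing the unscored item 2 is harmless.

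**Conclusion.** The concern holds in a conditional form. As printed, the table reverses all 36 items and gives two separately listed five-level groups one mapping. That at least one row is wrong is an inference from the split, to be confirmed in the cited manual. The role of the table relative to the software is unstated.

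The size depends on the route: no error if precoded answers are scored by the software; all eight scales backwards under double recoding; five to seven of eight wrong if the table is the only recoding. The last range assumes opposite-facing five-level rows, a correctly reversed item 7 and equal scoring steps. Each erroneous route contradicts the SAP's own 0-to-100 direction and carries through to the norm-based scales and both summaries.

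The documents do not support saying that the SF-36v2 results will be wrong. They support saying that the written rule permits it. Only this secondary instrument is at stake; BRFS and FACT-P do not use the table. It should be corrected before SF-36v2 scoring is programmed.

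**What to change.** Choose one of two wordings in Section 3.2.10:

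1. Delete the recoding table and state that precoded responses go unchanged into the vendor's scoring software. This is the simpler option.
2. Keep the table, correct its final values row by row against the SF-36v2 manual cited in Section 6, drop item 2, and state that the software must not recode again.

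Under either option, add a programming check: for each raw scale, a record with the best response to every item must score 100, and one with the worst response to every item must score 0. This exposes all the failures described here. If SF-36v2 scores have already been derived, run the same check on that program.

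The cost is a wording change and one short check. No data collection and no patient is affected.

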3.2.11. Visit windows

All data will be organised and analysed according to the scheduled visits outlined in the protocol. However, actual observation times may differ from the scheduled visit times and where this occurs the results should be allocated to the most appropriate visit. Therefore, time intervals (e.g. visit windows) have been constructed so that every observation collected after baseline visit can be allocated to a particular time point. If more than one record occurs within the same visit window where only one assessment is expected then the following rule should be applied (except for PSA and testosterone sample): for pre-study assessments only one record is expected and corresponds to the baseline visit; for post-treatment assessments the closest non-missing result to the scheduled visit should be used.

Scheduled visit	Time interval (days)
Baseline [V2]	1
Month 3 [V3]	2 to 138
Month 6 [V4]	139 to 229
Month 9 [V5] ^(a)	230 to 321
Month 12 [V6]	322 to 412
Month 15 [V7]	413 to 503
Month 18 [V8]	504 to 595
Month 21 [V9]	596 to 686
Month 24 [V10] ^(a)	687 to 777
Month 27 [V11]	778 to 868
Month 30 [V12]	869 to 960
Month 33 [V13]	961 to 1051
Month 36 [V14] ^(a)	1052 to 1142
X visit post Month 36 - Every 3 months	$((36+3*X-1.5)*30.4375+2)$ to $((36+3*X+1.5)*30.4375+1)$
Time interval (days): Date of visit – Date of baseline visit +1	
(a) sHRQoL assessment	

3.2.12. *Window for assessment for the PSA and testosterone parameters*

Testosterone (only in the triptorelin treatment group) should be assessed at 3; 6 and 9 months (± 14 days). At visit 3, evidence of lack of castration will be confirmed by a second test at least 2 weeks later.

PSA should be assessed every 3 month (± 14 days) except at Visit 2 (Baseline, Day 1 Month 0). Elevated PSA concentration (>0.2 ng/mL) must be confirmed by a second test 4 to 6 weeks later (acceptable delta of 14 days).

Scheduled visit	Time interval (days) for serum testosterone assessment		Time interval (days) for PSA Level assessment	
	As per protocol (± 14 days)	Used for analysis (Consecutive intervals)	As per protocol (± 14 days)	Used for analysis (Consecutive intervals)
Month 3 [V3] ^(a,b)	78 to 106	2 to 138	78 to 106	2 to 138
Month 6 [V4] ^(a,b)	170 to 198	139 to 229	170 to 198	139 to 229
Month 9 [V5] ^(a,b)	261 to 289	230 to 321	261 to 289	230 to 321
Month 12 [V6] ^(b)	--	--	352 to 380	322 to 412
Month 15 [V7] ^(b)	--	--	444 to 472	413 to 503
Month 18 [V8] ^(b)	--	--	535 to 563	504 to 595
Month 21 [V9] ^(b)	--	--	626 to 654	596 to 686
Month 24 [V10] ^(b)	--	--	718 to 746	687 to 777
Month 27 [V11] ^(b)	--	--	809 to 837	778 to 868
Month 30 [V12] ^(b)	--	--	900 to 928	869 to 960
Month 33 [V13] ^(b)	--	--	991 to 1019	961 to 1051
Month 36 [V14] ^(b)	--	--	1083 to 1111	1052 to 1142

Time interval (days): Date of assessment – Date of baseline visit +1
 (a) serum testosterone assessment
 (b) PSA Level assessment

3.2.13. *Rules and data formats*

Data will be presented using an appropriate number of decimal places (i.e. the number of decimal places used does not imply undue precision). Raw data will be presented to the number of decimal places collected, and derived data will be presented to an appropriate number of decimal places. The appropriate number of decimal places will be determined by general practice, mathematical rationale or scientific rationale (e.g. age should be presented in whole numbers).

For summary statistics, the following will be presented: n, arithmetic mean, standard deviation, median, first quartile, third quartile, minimum and maximum.

Mean, median, quartiles and standard deviation values will be reported to one decimal place greater than the raw/derived data that they summarise. Minimum and maximum values will be reported with the same precision as the raw data.

Percentages will be reported to one decimal place and 0% will not be presented. Percentages will be calculated using a denominator of all patients in a specified population with non-missing observations. The denominator will be specified in a footnote to the tables for clarification if necessary.

P-values will be reported to three decimal places (e.g.: $p=0.037$), after rounding. P-values which are less than 0.001 will be presented as '<0.001'.

All values below or above a limit of detection (e.g. <0.1 or >100) will be listed as such. In summaries of data values below limit of detection will be set to the limit of detection. Values above limit of detection will be set to limit of detection.

All text fields must be left justified and numeric or numeric with some text specification (e.g.: not done, unknown, <4.5, ...) must be decimal justified. Dates and times will be presented in the format as defined in the data-base, i.e. [ddmmmyyyy] and [hh:mm] respectively.

3.2.14. Pooling of Centres

It is not planned to perform a subgroup analysis on individual or groups of centres. To compute hazard ratios on the primary endpoint a Cox Proportional hazard model will be fitted including treatment group, Gleason score, country and pooled centres. In each country, the centres with a randomized number of patients strictly above 10 will be pooled in one centre.

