3.2. Analysis methods

3.2.1. Efficacy

3.2.1.1. Primary efficacy analysis

The primary efficacy analysis will be performed after 61 BR events have been observed and this analysis will be repeated on the number of BR events observed until the end of study.

The primary efficacy analyses of BRFS will be performed on the ITT population (cf. Section 3.2.10 for derived BRFS).

An exploratory analysis will be performed on the mITT and PP population (only on the total number of BR at the end of the study).

BRFS will be provided by treatment group. A log-rank test (two-sided) will be used to compare BRFS time between the two treatment groups. The Kaplan-Meier method will be used to obtain the estimates of median BRFS associated with each treatment. The 95% CI of the median BRFS time will also be provided.

The syntax with SAS using the LIFETEST procedure will be:

CCI [REDACTED]

The Cox Proportional hazard model will be fitted to compute hazard ratios and the corresponding 95% CI with treatment group, country (China as reference), nested effect centre(country) (the largest centre as reference) and Gleason score on prostatectomy specimen (in categories: ≤ 6 / $= 7$ / ≥ 8 , with ≤ 6 considered as the reference) as fixed factors.

The syntax with SAS using the TPHREG procedure will be:

CCI [REDACTED]

Interactions between treatment group and each covariate (country, centre(country) and Gleason score) will be tested one by one in separate models as follows:

CCI

P-value of covariates effect as well as interactions effect will be provided. Interaction will be considered as suggestive if p-value < 0.20. Suggestive interaction will be kept:

CCI

The validity of the model will be checked as follows:

- *Check of hypothesis of proportional hazards (graphically),*

This check of hypothesis of proportional hazards can be performed using plots the log of negative log of estimated survivor functions versus the log of time.

The syntax with SAS using LIFETEST procedure will be:

CCI

If the curves are parallel then the hypothesis is checked.

Results will be presented in terms of hazard ratios associated with 95% CI and p-value for treatment group and each other fixed factors.

Survival curves for each treatment group will be plotted on the same graph. Median BRFS time for each group and number of events will be provided.

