Should there be a suggestive country*treatment interaction or a centre(country)*treatment interaction, BRFS will also be analysed respectively by country/centre in order to describe any possible country/centre effect. Similarly, should there be a suggestive Gleason score*treatment interaction, BRFS will also be analysed by Gleason score categories (≤ 6 / $= 7$ / ≥ 8 , with ≤ 6 considered as the reference) in order to describe treatment effect within each subgroup.

Sensitivity analyses:

If a patient had at least two consecutive missing visits before the BR, a sensitivity analysis will be performed by censoring this patient at the date of the last visit preceding the missing consecutive visits (cf Section 3.2.10 for derived BRFS).

If patients died (whatever the cause) without BR, a sensitivity analysis will be performed by considering the death as an event (cf Section 3.2.10 for derived BRFS).

If lost to follow-up (prior to BR) is $\geq 5\%$. Baseline characteristics will be compared between groups of lost to follow-up and the other patients. If the lost to follow-up baseline characteristics differ from those of the other patients (as shown by 95 % CI), a sensitivity analysis will be performed excluding the lost-to follow-up patients.

Sensitivity analyses will be performed on ITT population on the first 61 BR events and repeated on the number of BR events observed until the end of the study if there is a difference of at least 5% of number of events (i.e. ≥ 65 events). The Log-rank test will be provided as well as the Cox Proportional hazard model. The interactions will be tested only if suggestive interactions were founded in the main analysis.

The primary efficacy analyses are summarised in the table below:

	ITT population		mITT population	PP population
	61 BR events	All BR events	All BR events	All BR events
Main analysis	X ⁽¹⁾	X	X	X
Sensitivity analysis 1 (censoring of patients with missing visits)	X	X ⁽²⁾		
Sensitivity analysis 2 (death as an event)	X	X ⁽²⁾		
Sensitivity analysis 3 (excluding lost-to-FUP patients)	X	X ⁽²⁾		

(1) Primary analysis

(2) Only if the number of BR events observed until the end of the study is different of at least 5% (i.e. ≥ 65 events)

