3.2.1.2. Secondary efficacy analysis

The secondary efficacy analyses will be performed on the ITT population. In these analyses, no interaction will be tested for EFS, OS, disease-specific mortality and PSA doubling time. For serum testosterone, only patients in the triptorelin-treated group will be included in the analysis

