3.2.1.2.1. Event-Free Survival

EFS will be provided by treatment group (cf. Section 3.2.10 for derived EFS).
EFS will be compared between groups using the same analysis and strategy used for BRFS.

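### The centre-pooling rule is written in the reverse of its evident purpose: it merges centres with more than 10 patients and leaves those with 10 or fewer as separate levels of the BRFS Cox model

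*SAP*

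**What the plan says.** Section 3.2.14 applies pooling to the Cox model that gives the BRFS hazard ratio, with treatment, Gleason score, country and pooled centres as terms. The rule is that, in each country, "the centres with a randomized number of patients strictly above 10 will be pooled in one centre". It says nothing about centres with 10 or fewer randomised patients. No other section states the rule the other way round, and Section 5 (Changes from protocol) does not mention it.

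Section 3.2.1.1 describes the same model and includes a "nested effect centre(country) (the largest centre as reference"). It continues: "Interactions between treatment group and each covariate (country, centre(country) and Gleason score) will be tested one by one in separate models". The threshold is set there too: "Interaction will be considered as suggestive if p-value < 0.20". After a suggestive country or centre interaction, "BRFS will also be analysed respectively by country/centre in order to describe any possible country/centre effect".

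For the secondary time-to-event endpoints, Section 3.2.1.2 states that "no interaction will be tested for EFS, OS, disease-specific mortality and PSA doubling time". The main analysis is nevertheless carried over; for example, "EFS will be compared between groups using the same analysis and strategy used for BRFS". OS, disease-specific mortality and PSA doubling time have matching sentences.

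**The concern.** Centres are pooled so that a model does not carry levels too small to estimate. Read literally, this rule does the opposite: the centres that hold most of the patients and events become one block per country, and only the smallest centres keep their own coefficient. The SAP gives no reason for wanting that, and the analyses in Section 3.2.1.1 gain nothing from it.

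At stake are the centre adjustment of the Cox hazard ratio, the centre hazard ratios and p-values that Section 3.2.1.1 says will be reported, the treatment-by-centre screen, and the by-centre analysis that the screen can trigger. The same centre term would pass to the Cox models for EFS, OS, disease-specific mortality and PSA doubling time, as a main effect only.

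The trial is open (Section 1.2). If the direction is left for a programmer to interpret, the covariate structure may be settled after centre sizes and outcomes are known.

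**Working it through.** **Inputs.** From Sections 1.2.1 and 1.3.4: 226 patients, about 10 centres, 2 countries, 61 BRs, and 36-month relapse of 40% against 20%. From Section 3.2.14: the threshold of 10. From Section 3.2.1.1: Gleason score in three categories. The SAP gives no centre sizes.

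**The plan's own figure.** The pooling rule carries no computed figure. The event target does, and it reproduces. With exponential times, HR = ln(0.8)/ln(0.6) = 0.437. Schoenfeld's formula gives 4(1.960 + 1.282)²/(ln 0.437)² = 61.3 events, and 61 events give 89.9% power. Centre does not enter this calculation.

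**Which centres are merged?** The average centre has 226/10 = 22.6 patients, so a typical centre is above 10 and is merged.

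**Case 1: every centre exceeds 10.**
- As written, each country has one level. Centre within country has 2 − 2 = 0 df, and so does its interaction with treatment. The model reduces to treatment, country and Gleason score.
- Reversed, ten levels remain and centre within country has 10 − 2 = 8 df.

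**Case 2: some centres have 10 or fewer.** Each centre df then rests on one of those centres. Taking the overall BR fraction, 61/226 = 0.270, for every patient independently:
- Expected BRs in a centre of 10: 10 × 61/226 = 2.7, shared between two arms.
- Chance of no BR, (165/226)ⁿ: 0.389 for n = 3, 0.207 for n = 5, 0.043 for n = 10.

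A level without a BR has no finite Cox hazard ratio.

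**Illustration.** The layouts below are assumed. Each has 226 patients in ten centres, five per country. In the second and third, the pooled small centres exceed 10 in both countries, so no further merging is needed.

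| Layout | As written: levels; centre df; smallest level | Reversed: levels; centre df; smallest level |
|---|---|---|
| Even, 21 to 23 each | 115 / 111; 0 df; no separate centre | ten centres; 8 df; n = 21, 5.7 BRs, no-BR chance 0.1% |
| 60, 30, 15, 8, 4 / 50, 28, 16, 9, 6 | 105, 8, 4 / 94, 9, 6; 4 df; n = 4, 1.1 BRs, 28% | 60, 30, 15, 12 / 50, 28, 16, 15; 6 df; n = 12, 3.2 BRs, 2% |
| 90, 12, 6, 3, 2 / 80, 18, 8, 4, 3 | 102, 6, 3, 2 / 98, 8, 4, 3; 6 df; n = 2, 0.5 BRs, 53% | 90, 12, 11 / 80, 18, 15; 4 df; n = 11, 3.0 BRs, 3% |

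**What the screen can see.** As written, all centres above 10 in a country share one coefficient and one treatment interaction. A difference in treatment effect among them cannot appear in the test, whatever its size. Differences between countries stay visible, because treatment-by-country is tested separately.

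**Price of reversing.** With ten centres all above 10, the main model has treatment 1 + country 1 + centre 8 + Gleason 2 = 12 parameters, or 61/12 = 5.1 BRs each. The treatment-by-centre model has 12 + 8 = 20, or 61/20 = 3.1 each. As written, the same trial has 1 + 1 + 0 + 2 = 4 parameters, or 61/4 = 15.3 BRs each.

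**The case against.** **Intent is not stated.** This is true: the inversion is inferred from the rule's effect, and the separate status of small centres from silence. But no purpose visible in the SAP is served by the literal rule, and a rule that needs interpretation is not pre-specified.

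**The reach is assumed.** Section 3.2.14 ties pooling to the primary hazard-ratio model. The interaction tests and the secondary endpoints do not repeat the word pooled, and the SAS code is blacked out. This carries limited weight. Sections 3.2.1.1 and 3.2.14 describe the same Cox model, the interactions are with that model's covariates, and the secondary endpoints take over the same analysis.

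**The literal rule gives a leaner model.** This stands when all centres exceed 10: 4 parameters against 12. But a model without centre could be specified openly, and the literal rule does not give one reliably, because it keeps the sparsest centres whenever there are any.

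**Stronger readings that the document does not support.**
- A reader might infer that the primary result is compromised. The primary test is a log-rank test described without centre.
- A reader might take the choice of the largest centre as reference to contradict the rule. It does not; the merged block can serve as the largest level.
- A reader might set "It is not planned to perform a subgroup analysis on individual or groups of centres" against the conditional by-centre analysis in Section 3.2.1.1. That is a clerical matter of wording: one sentence concerns planned subgroups, the other a descriptive follow-up.
- A reader might want a figure for the power that the screen loses. It would depend on centre sizes and a test type that the visible text does not give, and on how an undersized pooled group is handled. None is offered here.

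**Conclusion.** The sentence is wrong as written and should be corrected; the importance is minor to moderate. The structural result needs no assumption about centre sizes: the centre term either vanishes (0 df, against 8 for ten centres in two countries) or rests only on centres of at most 10 patients. The event figures assume the overall BR fraction of 61/226 in every centre.

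The damage is confined to the centre adjustment, the centre estimates, the interaction screen and the by-centre analysis. The log-rank test and the 61-event calculation are untouched. The adjusted treatment hazard ratio should change little, because treatment is randomised and centre is a nuisance covariate; this is an expectation, not a result derived from the SAP. The correction lets the screen see the larger centres but does not make it a strong test: with about 20 parameters for 61 BRs, the interaction p-value remains weak evidence.

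**What to change.** Replace the last sentence of Section 3.2.14 with: *In each country, centres with 10 or fewer randomised patients will be pooled into one centre; centres with more than 10 are kept separate.* State, before database lock, what happens if the pooled group still has 10 or fewer patients; merging it with the smallest remaining centre in that country is one option.

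The cost is a sentence and a fallback rule, with no new data and no change to the primary test. The downside is the larger model shown above, so the treatment-by-centre result should be read cautiously.
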